Study Protocol

Study Title: Wellness Programs for Brain-Injured Individuals

NCT#: 02600637

Date: 4-5-2019

Study Protocol

Behavioral Protocol

Participants will be recruited from [name] large stroke research participant pool at VA Northern California. Individuals in our research pool have current brain MRI scans, have been thoroughly screened for prior medical and psychiatric history, and have already been evaluated on a large neuropsychological battery, which will facilitate the execution of the current proposal in a relatively short timeframe. Participants in our pool sign consent forms that include permission to use their neuropsychological and imaging data for future related studies. If additional research participants are needed, we will recruit patients from our VA Outpatient Neuropsychology and NeuroBehavior Clinics, and the Neurocognitive Rehabilitation Unit in our CLC, with the assistance of our collaborators who run these clinics, VA Staff Neurologist, [name] and VA Staff Geropsychiatrist, [name]. If needed, patients can also be identified through automated digital searches of VA-CPRS medical records and contacted with IRB-approved letters to eligible participants, as we have done successfully in the past.

Treatment Interventions. Participants will be randomly assigned to either the MBSR or Brain Health control intervention. Although this is a pilot study, inclusion of a control group is highly recommended in order to evaluate all potential procedures for a larger-scale efficacy trial. Randomization will be achieved with freely available software, using covariate adaptive randomization to ensure groups of equal sizes that are balanced for age, education, side of stroke (left vs. right hemisphere), lesion volume, months post-stroke, current cognitive status (based on the Mini-Mental State Examination), and baseline anxiety and depression levels.

Half of the study participants will complete an 8-week Mindfulness-Based Stress Reduction (MBSR) program on our VA campus. The course will be led by a certified MBSR instructor who has received extensive training in mindfulness-based interventions and specifically in MBSR. He has already led multiple groups of brain-injured Veterans through the program on our VA campus. The MBSR group meets once per week for 2½ hours, with a day-long retreat for 7½ hours in the 6th week of the program. Participants are instructed in mindfulness practice in the form of sitting meditation, body awareness and mindful movement, and informal mindfulness practices of daily life (e.g., eating, communicating, working, coping). Between classes, patients enhance their participation by practicing at home with meditation CDs, homework assignments, and readings from the course materials and textbook. Home practice is tracked with pre-made logbooks (used in our prior study) that patients keep for the duration of the study and record the number of hours engaged in practice at home. Logbooks are checked and recorded by study staff each week.

The other half of participants will take part in an active control intervention, a Brain Health program, which is matched for the same number of hours, instructor, schedule, homework, and home practice as the MBSR program. The Brain Health program has been used previously on our VA campus by collaborator [name] as an active control intervention for cognitive rehabilitation research protocols. It includes background and education about brain-behavior relationships and discusses how brain injuries can disrupt various aspects of cognition, such as memory and attention. We have found that our Brain Health program is the appropriate control intervention because it matches for critical process elements such as clinician interaction, social interaction with the group, and homework activities, without the inclusion of a reflection/mindfulness component, which is hypothesized to be the critical factor for improving functioning.

A battery of standardized psychological and cognitive measures will be administered 1) prior to the intervention (pre-testing) and 2) within one week following the intervention (post-testing). All

pre- and post-testing will be conducted by a licensed neuropsychologist who will be blinded to the participant's intervention condition (MBSR vs. Brain Health/Education). The battery includes the Geriatric Depression Scale, State-Trait Anxiety Inventory, and Repeatable Battery for the Assessment of Neuropsychological Status (RBANS).

## **Statistical Analysis Plan**

**Study Title:** Wellness Programs for Brain-Injured Individuals

**NCT#:** 02600637

**Date:** 4-5-2019

***Behavioral Data.*** First, recruitment feasibility will be measured by tracking the total number of potential patients contacted, the number who indicate a willingness to participate, and the number who meet inclusion/exclusion criteria. Based on recommendations for pilot intervention studies, the feasibility criterion for recruitment will be a minimum of 70% of eligible patients recruited from the available research participant pools. Retention will be based on the percentage of recruited patients who complete all components of the program, and our criterion will be 70% retention rates in both the MBSR intervention and Brain Health groups.

Criteria for effective participation in both the MBSR and Brain Health program are: a) all participants attending  $\geq 70\%$  of the sessions; b) all participants logging an average of  $\geq 3$  hours of practice/homework per week; and c) comprehension of course material as reflected by a score of  $\geq 75\%$  correct on a written quiz during post-testing. Treatment fidelity will be assessed by videotaping the instructor during the intervention and control sessions, and independent clinicians with extensive familiarity with the programs will rate a random sample of four sessions on a scale of 1-5, with higher numbers indicating better adherence to the manuals. The effectiveness of our blinding procedures will be evaluated with a forced-choice recognition test at the end of the study that asks the neuropsychologist doing the pre- and post-assessments to indicate which group (MBSR or Brain Health) a participant belongs to and how confident they are in their assessment. Randomization procedures will be evaluated by analyzing the demographic summary tables generated, comparing values between the MBSR and Brain Health groups.

With respect to study safety, a definitive determination of intervention safety can only be made with a much larger sample size (not as part of a pilot study), but our study criterion is that serious adverse events will be brought to the attention of Mental Health and reported to the VA IRB within 24 hours of occurring.

Acceptability will be measured with the same questionnaire used in our previous study of MBSR in Veterans with a history of mTBI to evaluate patients' satisfaction and the tolerability of the program. The intervention will be considered acceptable if: 1) the average response for each question is  $\geq 4.0$  out of 5 (e.g., "How satisfied were you with this program?"); and 2) 80% or more of the participants rate at least one course component with a score of  $\geq 7$  out of 10 (e.g., meditation, group discussions). The questionnaire also includes open-ended questions regarding the participants' experience in the research study overall (e.g., "Have there been any positive changes in your medical condition?"). These responses will be analyzed using freely available content analysis software to identify common themes (e.g., program is enjoyable; sessions are too long).

A battery of standardized psychological and cognitive measures will be administered 1) prior to the intervention (pre-testing) and 2) within one week following the intervention (post-testing). All pre- and post-testing will be conducted by a licensed neuropsychologist who will be blinded to the participant's intervention condition (MBSR vs. Brain Health/Education). Our primary outcome target for Aim 2 will be a reduction in depression and anxiety scores from pre- to post-MBSR intervention. Outcome measures include the Geriatric Depression Scale and the State-Trait Anxiety Inventory. These measures have been shown to have strong reliability and validity and are most appropriate for the current study, given the demographics of our sample. Our secondary outcome target for Aim 2 is a change in cognitive performance as assessed by Repeatable Battery for the Assessment of Neuropsychological Status.

Since using inferential statistics to assess treatment effects is not appropriate for pilot studies, we will preliminarily report descriptive statistics. Just as a point of reference, however, the type of inferential statistics we would use for a subsequent, efficacy study of MBSR would be a mixed

model-random effects analysis for longitudinal data that would include all participants who completed the baseline assessment and at least one session following intervention (including those with incomplete data), which would reduce attrition bias and increase generalizability, power, and precision. Treatment group, time, and their interaction would be the primary fixed effects in the model. Number of classes attended would be considered as an additional factor, and the model would assume ignorable attrition and would not take an intention-to-treat approach. The key value for hypothesis testing would be the group-by-time interaction term.

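### Does the 70% retention criterion need a definition of programme completion, and a stated link to the attendance criterion?

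*SAP*

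**What the plan says.** The first paragraph of the SAP's Behavioral Data section defines retention: "Retention will be based on the percentage of recruited patients who complete all components of the program". The threshold follows: "our criterion will be 70% retention rates in both the MBSR intervention and Brain Health groups".

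The next paragraph introduces a different measure: "Criteria for effective participation in both the MBSR and Brain Health program are: a) all participants attending" at least 70% of the sessions. Home practice has a similar form, "b) all participants logging an average of" at least 3 hours a week. A third item is a score of at least 75% "correct on a written quiz during post-testing".

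The Treatment Interventions section of the Protocol gives the schedule: an 8-week course ("The MBSR group meets once per week for" two and a half hours) with a day-long retreat in week 6. It does not say whether the retreat counts as a separate session. The control course is described as matched on hours, schedule, homework and home practice.

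The word component appears twice more in connection with the courses. The SAP's acceptability paragraph uses it for a satisfaction item: "80% or more of the participants rate at least one course component with a score of" at least 7 out of 10. The Protocol uses it to say how the control course differs: "without the inclusion of a reflection/mindfulness component". Neither use defines completion.

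**The concern.** Two things look unfinished.

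First, the numerator of the retention rate is open. Completing everything could mean attending every class and the retreat, or it could mean reaching some sufficient level of attendance. The same attendance records could put an arm below 70% on one reading and above it on the other, and the choice is not fixed before the data are seen.

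Second, the retention rule tolerates up to 30% non-completers, while the attendance criterion is worded for all participants. If that means everyone recruited, one person who leaves before reaching 70% of sessions fails the criterion in an arm that may still pass on retention. If it means only those retained, the criterion is met automatically whenever completion requires at least 70% of sessions.

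This is a pilot meant to try out procedures for a larger trial, and treatment outcomes are only described. The feasibility thresholds are therefore its main pre-set pass or fail statements, which makes loose wording in one of them worth checking.

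**Working it through.** The plan gives no sample size, expected attendance or expected drop-out, so there is no stated figure to reproduce. The check separates what follows from the text alone from what needs assumptions.

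**From the text alone**

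- Sessions: 8, or 9 if the retreat is counted separately.
- Attendance criterion: 0.7 × 8 = 5.6, so at least 6 of 8; 0.7 × 9 = 6.3, so at least 7 of 9. Either way a person may miss two sessions.
- That person is not retained if every session is required, but would be if the 70% level counts as completion. So the reading can change who is counted.
- Retention threshold for an arm of 10, 15 or 20 (sizes chosen for illustration): at least 7, 11 or 14 retained, so 3, 4 or 6 non-completers are allowed. The attendance criterion, applied to everyone recruited, allows nobody below 70%. A person who leaves after session 6 of 8, or 7 of 9, still meets it.

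**How far the reading could matter, under assumptions**

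Assume 9 sessions, 15 per arm, and the same attendance probability q at each session, independent across sessions and people. Then:

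- P(every session) = q^9
- P(at least 7 of 9) = sum over k = 7 to 9 of C(9,k) q^k (1−q)^(9−k)
- P(arm reaches 70%) = sum over j = 11 to 15 of C(15,j) p^j (1−p)^(15−j), with p equal to one of the two probabilities above

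| q | every session | at least 7 of 9 | arm passes, every session | arm passes, at least 7 of 9 |
|---|---|---|---|---|
| 0.80 | 0.134 | 0.738 | 0.000 | 0.647 |
| 0.90 | 0.387 | 0.947 | 0.007 | 0.999 |
| 0.95 | 0.630 | 0.992 | 0.295 | 1.000 |

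Over 8 or 9 sessions, q from 0.80 to 0.95 and 10 to 20 per arm, the chance that one arm passes runs from about 0 to 0.55 on the strict reading and from 0.65 to 1.00 on the lenient one. Clustering of absences within people narrows the gap: with an intra-person correlation of 0.10 and q = 0.90 (beta-binomial, 9 sessions), the two shares are 0.509 and 0.894.

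For the second point, assume 15 per arm, 10% leaving, all before the 70% mark and nobody else failing. Retention passes with probability 0.987, and the attendance criterion applied to everyone recruited passes with probability 0.9^15 = 0.206.

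**Whether the missing words block the analysis**

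- The attendance criterion cannot be scored without each participant's session count. The same count gives the share attending every session and the share attending at least 70%, so both versions of retention can be computed with no further data.
- Two other possible meanings of component are weak. Both documents place post-testing after the intervention, so it does not sit naturally among the components of the programme; the quiz is merely taken at that visit. The satisfaction item and the description of the control course do not concern completion. Even if content differs by arm, each arm completes its own course, and the Protocol matches the two on hours, schedule and homework.
- Retention asks how many stay; effective participation asks how fully people take part. Failing the second while passing the first is an informative pilot result, not an inconsistency.

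**The case for a change.** The strongest case for a change is that a pass or fail threshold is worth little if its numerator can be chosen once attendance is known. The calculations above show that the choice could decide the result, and a sentence or two in the SAP would settle it at almost no cost. The literal reading does not fully close the question either: it is unclear what completing the home practice or the readings would mean, and requiring every session is stricter than the attendance the SAP accepts as effective participation.

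Much of this stands. Completion is undefined, the population for the attendance criterion is unstated, and a definition would make the document tidier. What does not stand is that the plan would mislead without it. Neither document makes the retention result trigger anything. The SAP confines treatment effects to descriptive statistics, so no test or estimate depends on who is labelled retained. A report that gives attendance counts lets any reader apply either definition. The further suggestion, to report post-test completion by arm without a threshold, would be a reasonable extra table row, but it is a different measure and does not define completion.

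**Conclusion.** No change to the plan follows. The text leaves a real but minor ambiguity: completion could mean every session or a sufficient level of attendance, and the attendance criterion could cover all recruited or only those retained. The two criteria do not contradict each other, and no number in the SAP is wrong.

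The certain part is small: someone who misses one or two of 8 or 9 sessions is classified differently under the two readings. The larger differences in the chance of passing rest on assumed arm sizes, attendance, leaving rates and independence, none of which the documents give. They show that the reading could matter, not that it will.

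The conclusion rests on three features of the plan: session counts must be kept in any case, the results are descriptive, and no decision rule depends on retention. If retention were later made a condition for going on to the larger trial, the definition would have to be fixed beforehand. As the documents stand, an analyst can state the reading used, show the counts, and lose nothing.

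### The Aim 2 primary target is a before-to-after fall with MBSR, with no reference to the randomised Brain Health arm, so change common to both arms could produce it

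*SAP*

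**What the plan says.** In the Aim 2 paragraph of the SAP (Behavioral Data) the primary target reads: "Our primary outcome target for Aim 2 will be a reduction in depression and anxiety scores from pre- to post-MBSR intervention". The measures are the Geriatric Depression Scale (GDS) and the State-Trait Anxiety Inventory (STAI). The secondary target is a change on the RBANS, with neither arm named. The SAP then rules out inferential statistics for treatment effects in a pilot and promises descriptive statistics. It does not say whether these will be given by arm, and it names no difference. The mixed model with its group-by-time term is set out only to show what a subsequent efficacy study would use.

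Elsewhere the SAP names both arms where it means both. For retention, for example, "our criterion will be 70% retention rates in both the MBSR intervention and Brain Health groups".

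The Protocol (Treatment Interventions) randomises participants to MBSR or Brain Health in equal groups, balanced on several factors including "current cognitive status (based on the Mini-Mental State Examination), and baseline anxiety and depression levels". Brain Health is "matched for the same number of hours, instructor, schedule, homework, and home practice as the MBSR program". The Protocol defends this choice of control on the ground that it shares contact with a clinician, contact with the group and homework with MBSR. What the control leaves out is also stated: it runs "without the inclusion of a reflection/mindfulness component, which is hypothesized to be the critical factor for improving functioning". A blinded neuropsychologist gives the same battery before and after the intervention.

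**The concern.** The Protocol's hypothesis about the mindfulness component concerns a contrast between arms, but the primary target looks at one arm. A fall in MBSR scores combines any effect of MBSR over Brain Health with whatever both arms share: repeat testing, instructor and group contact, homework, the passage of time, and possibly regression to the mean. As worded, the target cannot separate these, even though the design collects the data needed to do so.

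What is at stake is what the pilot can say about Aim 2. Feasibility, retention, participation and acceptability criteria are not affected.

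**Working it through.** **Is there a between-arm quantity for these outcomes in this trial?** The places to look are these.

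- Aim 2 primary target: MBSR only.
- Aim 2 secondary target: no arm named.
- Descriptive-statistics sentence: no arm and no difference named.
- Group-by-time interaction: between-arm, but for a later study.
- Comparison of summary tables between arms: planned for this trial, but for demographics, to check randomisation.

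None commits this trial to a between-arm summary of GDS or STAI.

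**Illustration of size.** The plan has no figure to reproduce. All inputs are assumptions, in SD units: n per arm, r the pre/post correlation, and g the improvement shared by both arms. The true difference between arms is set to 0, and clustering by class group is ignored.

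Formulas, with n = 15, r = 0.6:

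- SE of the within-MBSR fall = √(2(1−r)/n) = √(0.8/15) = 0.231
- SE of the post-test difference adjusted for baseline = √(2(1−r²)/n) × √((2n−3)/(2n−4)) = √(1.28/15) × √(27/26) = 0.298
- SE of the difference in change = √(4(1−r)/n) = √(1.6/15) = 0.327

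With g = 0.3:

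- Probability that the MBSR mean falls at all = Φ(0.3/0.231) = 0.903.
- Expected MBSR fall 0.30; expected between-arm difference 0.

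Taken as estimates of MBSR versus Brain Health, the quantities compare as follows. Break-even is the shared change above which the between-arm quantity has the smaller total error: g = √(SE_between² − SE_within²).

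| Quantity | Bias | SE | RMSE | Break-even g |
|---|---|---|---|---|
| Within-MBSR fall | 0.30 | 0.231 | √(0.30² + 0.231²) = 0.379 | – |
| Baseline-adjusted difference | 0 | 0.298 | 0.298 | 0.188 |
| Difference in change | 0 | 0.327 | 0.327 | 0.231 |

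Over n = 10, 15, 20 and r = 0.5, 0.6, 0.7, break-even runs from 0.150 to 0.244 SD for the adjusted difference and from 0.173 to 0.316 SD for the difference in change. A simulation of 100,000 trials at n = 15, r = 0.6, g = 0.3 agreed: mean within-arm change −0.300 (SD 0.231), probability of a fall 0.902, mean adjusted difference 0.000 (SD 0.297).

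**Sensitivity of the probability of a fall.** For n = 10 to 30 per arm and r = 0.5 to 0.8, it is 74% to 96% with a shared fall of 0.2 SD, and 83% to over 99% with 0.3 SD. With no true change in either arm it is 50%, because the SAP sets no minimum fall.

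**The case against.** The strongest reply is that the sentence names outcomes and an expected direction, and is not an analysis. In a two-arm pilot, descriptive statistics offered in place of inference on treatment effects most naturally means scores by arm and time, mirroring the later model. The Protocol also gives the control a procedural purpose: "inclusion of a control group is highly recommended in order to evaluate all potential procedures for a larger-scale efficacy trial". The SAP disclaims inference, attaches no decision rule or efficacy claim to the target, and already recognises group-by-time as the key term. Aim 2 is not defined in these documents.

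This is a plausible reading, and it limits the consequence. It does not change the target: even with both arms tabulated, the result could be read from the MBSR column alone.

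Further points stand:

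- The SAP never proposes the within-arm fall as an estimate of MBSR versus Brain Health. The error comparison shows what happens if a reader uses it that way.
- The between-arm quantity is noisier and does not win everywhere. At n = 10, r = 0.5, g = 0.3 the difference in change has RMSE √(4 × 0.5/10) = 0.447, against √(0.3² + 2 × 0.5/10) = 0.436 for the within-arm fall. Below break-even the within-arm fall is closer on average, though biased.
- The documents show no selection on high depression or anxiety scores, so regression to the mean is possible but not demonstrated.
- A restated target without a minimum size would still favour MBSR half the time under no effect. It should be reported as an estimate, not as met or unmet.
- The contrast would not isolate mindfulness. Brain Health has content of its own: "It includes background and education about brain-behavior relationships and discusses how brain injuries can disrupt various aspects of cognition".

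**Conclusion.** The concern holds. The wording shows it without any calculation: the primary target uses one arm, and nothing in the plan for this trial ties it to the other. A shared improvement enters the within-MBSR fall in full as bias and cancels from the between-arm difference. The figures above show how large this could be under assumed inputs; the conclusion does not rest on them. The point merits correction but is modest in consequence, because the pilot is descriptive and no decision depends on the target. For RBANS the fault is one of ambiguity, since that target names no arm.

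**What to change.** Restate the Aim 2 primary target as the MBSR minus Brain Health difference on GDS and on STAI. Use either the post-test difference adjusted for the baseline score on the same scale or the difference in pre-to-post change, and state which; under the assumptions used here the adjusted difference is the more precise. Report it descriptively, with n, mean and SD by arm and no hypothesis test; a 95% confidence interval to show precision is optional. Treat RBANS the same way.

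Keep within-arm changes as supporting description. Add two statements: that a fall within MBSR alone is not evidence of an MBSR effect, and that the contrast is MBSR versus brain-health education.

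The cost is a few lines of SAP wording and one table, from data already to be collected. The drawback is a headline that is likely to be less favourable and will be imprecise.

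### Does the SAP's mixed model, restricted to participants seen after the intervention and not intention-to-treat, need rewriting because it cannot reduce attrition bias?

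*SAP*

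**What the plan says.** The SAP's Behavioral Data text separates what this trial will do from what a later one might do. For this trial: "Since using inferential statistics to assess treatment effects is not appropriate for pilot studies, we will preliminarily report descriptive statistics". The model is then introduced with the words "Just as a point of reference, however, the type of inferential statistics we would use for a subsequent, efficacy study of MBSR".

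That reference model is a random-effects analysis of longitudinal data with group, time and their interaction as the primary fixed effects. The interaction is the term to be tested. Three features attract attention:

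- The analysis set and the benefit claimed for it: "all participants who completed the baseline assessment and at least one session following intervention (including those with incomplete data), which would reduce attrition bias".
- The missing-data assumption and the estimand: "the model would assume ignorable attrition and would not take an intention-to-treat approach".
- A variable measured after randomisation: "Number of classes attended would be considered as an additional factor".

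The only assessment schedule in either document is the pilot's own: one battery before the intervention and one within a week after it.

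**The concern.** Read against the pilot's schedule, the paragraph seems to contradict itself. If there is one post-test and a session means an assessment, then requiring a baseline plus at least one session afterwards leaves only people with both scores. The parenthesis about incomplete data adds nobody for a given outcome, and those lost to attrition are exactly those removed. A likelihood-based model corrects for dropout that depends on baseline only if the dropouts' baseline scores stay in it, so the stated set also undermines the SAP's own assumption of ignorable attrition.

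Attendance is a second worry. It may be affected by arm and by motivation, so conditioning on it can stop the interaction from estimating the effect of assignment. The paragraph also names none of the covariates used to balance the randomisation.

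If the model supplied this trial's treatment comparison, the key term could carry a bias that randomisation was meant to prevent.

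**Working it through.** The documents give no sample size, SD, effect size or alpha, so there is no stated figure to reproduce. All numbers below rest on assumptions: unit SD, no true effect unless stated, and roughly 30% lost. That 30% is not a dropout tolerance in the plan. The SAP's 70% retention criterion counts people completing all program components, not people with a post-test.

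**1. One post-test.** With pre/post correlation r, the expected change given baseline x is −(1 − r)x. The mean change among completers is therefore −(1 − r) times their mean baseline.

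- Let dropout follow a logistic curve with intercept −1 and slope 1 per SD, rising with baseline in one arm and falling in the other. Integration gives 70% retained and completer baseline means of −0.255 and +0.255.
- Bias in group-by-time at r = 0.6: 2 × 0.4 × 0.255 = 0.204 SD. A simulation with 200,000 per arm gave 0.208 for the stated set, 0.208 for complete cases (the same people) and 0.005 for everyone with a baseline.
- A milder case has baseline-related dropout in one arm only and random dropout in the other. The bias is (1 − r) times the shift in completer mean baseline. The shift is 0.143 for a slope of 0.5 and 0.375 for a slope of 2, so the bias runs from 0.3 × 0.143 = 0.043 (r = 0.7) to 0.5 × 0.375 = 0.187 (r = 0.5).

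**2. Two post-tests.** Bias in group-by-time at the last visit, maximum likelihood with unstructured covariance, in SD:

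| Dropout pattern | Correlations | Stated set | Complete cases | All with baseline |
|---|---|---|---|---|
| On last score, opposite by arm | 0.6 throughout | 0.118 | 0.110 | 0.000 |
| On last score, opposite by arm | 0.5 pre-post, 0.8 post-post | 0.151 | 0.057 | 0.005 |
| Early loss random, late loss on first post score, opposite by arm | 0.5, 0.8 | −0.003 | −0.090 | −0.005 |
| On last score, same in both arms | 0.5, 0.8 | 0.003 | 0.002 | 0.001 |

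The stated set removes the bias in the third row, is no better in the first, is worse in the second, and makes no difference in the fourth.

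**3. Dropout depending on the unseen score.** Every set is biased. With one post-test: −0.206 (stated set and complete cases) and −0.346 (all with baseline). With two, correlation 0.6: −0.164, −0.118 and −0.243 for stated, complete and all.

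**4. Attendance.** The assumed true group-by-time effect is −0.30, MBSR attends one class fewer, and a hidden trait u raises the post score by 0.5u and lowers attendance by 0.9u (residual attendance SD 0.7). Data are complete.

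- As a main effect, attendance is constant within a person and cannot alter the difference in change. The fitted interaction was −0.290 with and without it.
- As attendance-by-time, the slope of change on attendance is −0.45/(0.81 + 0.49) = −0.346. The adjusted effect is −0.30 − (−0.346)(−1) = −0.646; the fitted value was −0.643.

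The SAP does not say which form it means, and says only that attendance would be considered.

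**5. Which of these results reaches the trial?** The model is not among this trial's analyses, and the later study's visits are not given. Steps 1 to 4 therefore describe a possible future analysis and change no planned table here.

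**The case for a change.** The strongest case for acting is that the Protocol justifies its control group by the need to try out procedures for a larger efficacy trial. This is the only inferential model in the SAP and could be copied forward. The claim of less attrition bias is unqualified and has no stated comparator. On the only documented schedule it is wrong relative to complete cases, and rewording costs little.

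Much of that stands as advice for the later protocol. There, it would be better to keep every randomised participant with a baseline, analyse as assigned, define session, name the comparator and treat attendance as supplementary.

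It does not carry over to this plan. Longitudinal data and at least one later session read naturally as a design with several post-intervention visits, where the claim can hold. Declaring the analysis not intention-to-treat is an open choice of estimand and does not by itself prove attrition bias. Naming the primary fixed effects does not rule out covariates, and the later study's randomisation is unknown. Adding baseline severity as a covariate when baseline is already a response would put the same score on both sides.

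Two suggestions would touch the pilot: seeking post-tests from everyone, and fixing the population for the descriptive tables. Neither corrects a contrary rule. No section limits post-testing to attenders or applies the reference model's population to the pilot's tables. An analyst would ordinarily show the number assessed by arm at each time and describe change in those with both scores.

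**Conclusion.** No change to the plan. The criticism is correct conditionally: with a single post-test, the stated set equals the completers and offers no protection beyond a complete-case analysis. The cost would be about 0.2 SD if dropout ran in opposite directions by arm, and 0.04 to 0.19 SD if it was baseline-related in one arm only. An attendance-by-time term would also distort the interaction; a main effect need not. These sizes depend on assumed dropout and attendance patterns that nothing in the documents establishes, and in the scenario with the same dropout in both arms the bias was about zero.

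For this trial the consequence is nil. Its treatment outcomes are reported descriptively, and rewriting a model that will not be fitted alters no estimate or conclusion. What remains is loose wording in an illustrative paragraph, to be settled when the efficacy study has its own visit schedule and SAP.
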